6.1. Inclusion Criteria

The following patients will be enrolled

Recent (≤ 2 weeks prior to randomization) - Confident COVID-19 diagnosis confirmed by antigen detection test and/or PCR and/or positive serology, or any emerging and validated diagnostic laboratory test for COVID-19 within this period.

-In some patients, it may be impossible to get a confident laboratory confirmation of COVID-19 diagnosis after 24h of hospital admission because viral load is low and/or problems with diagnostic sensitivity. In those cases, in absence of an alternative diagnosis, and with highly suspect bilateral ground glass opacities on recent (< 24 h) chest-CT scan (confirmed by a radiologist and pulmonary physician as probable COVID-19), a patient can be enrolled as probable COVID-19 infected. In all cases, this needs confirmation by later seroconversion.

-Presence of acute hypoxic respiratory failure defined as (either or both)
saturation below 93% on minimal 2 l/min O₂
PaO₂/FiO₂ below 350

-Admitted to specialized COVID-19 ward

-Age 18-80

-Male or Female

-Willing to provide informed consent

6.2. Exclusion Criteria

-Patients with known history of serious allergic reactions, including anaphylaxis, to human granulocyte-macrophage colony stimulating factor such as sargramostim, yeast-derived products, or any component of the product.

-mechanical ventilation before start of study

-Patients enrolled in another investigational drug study

-Pregnant or breastfeeding females (all female subjects regardless of childbearing potential status must have negative pregnancy test at screening)

- patients with peripheral white blood cell count above 25.000 per microliter and/or active myeloid malignancy

-patients on high dose systemic steroids (> 20 mg methylprednisolone or equivalent) for COVID-19 unrelated disorder

-patients on lithium carbonate therapy

-Patients with serum ferritin > 2000 mcg/L (which will exclude ongoing HLH)

6.2.1. Screen failures

Screen failures are defined as subjects who consent to participate in the clinical study but are not subsequently randomly assigned to the study intervention or entered in the study. A minimal set of screen failure information will be kept to ensure transparent reporting of screen failure subjects.

7. Target Population

7.1. Subjects

7.1.1. Number of subjects and planned recruitment rate

There is a large number of COVID-19 infected patients that are currently being hospitalized across the globe. In just 9 days time, our COVID-19 ward at Ghent University Hospital has admitted 25 confirmed cases, of which a significant portion (50%) already fulfill eligibility criteria for the current proposed protocol. Similar numbers of patients are currently being seen in all centers. We therefore believe that given the current ascending part of the epidemiology curve, with numbers of patients rising sharply, there will be no shortage of patients that are eligible.

The number of subjects that will be included in this study is: 80.
These are divided into following sub-groups:

Group A : active **sargramostim** treatment group, treatment for initial 5 days, no deterioration after 5 days

Number of patients : 40

Group B : control group : no treatment with sargramostim in first 5 days

Number of patients : 40

Group C and D :

Data from the Wuhan COVID-19 epidemic show that patients that deteriorate are facing a prolonged period of mechanical ventilation. Therefore, from day 6 onwards, progressive patients in the active group will have the option to receive an additional 5 days of IV sargramostim 125mcg/m² body surface area once daily, based on the treating physician's assessment. This group will be called group C. It is estimated that some 30% of patients might deteriorate and require non-invasive or invasive mechanical ventilation, giving potentially rise to 12 patients that progress from group A to group C, if the clinician decides to move forward with the drug.

In the control group progressing to requiring non-invasive or invasive mechanical ventilatory support, from day 6 onwards, the treating physician will have the option to initiate IV sargramostim 125mcg/m² body surface area once daily for 5 days. This group will be called group D. It is estimated that some 30% of patients might deteriorate to mechanical ventilation or ARDS, giving potentially rise to 12 patients that progress from group A to group C, if the clinician decides to move forward with the drug

Comparisons between group A (early sargramostim) versus group B (no sargramostim) at day 6 will be important for reaching primary endpoint, and for key secondary endpoints. Comparisons of Group A (early 5 day intervention with sargramostim) with Group D (late 5 day intervention with sargramostim) will also be very informative for secondary endpoint analysis.

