1.4. Subjects

1.4.1. Number of subjects

A total of 80 patients with confirmed COVID-19 and acute hypoxic respiratory failure will be enrolled, 40 in the active and 40 in the control group.

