9.1. Randomization

In this open label trial patients will be randomized in a 1:1 ratio. Randomization in Belgium will be done using REDCap (electronic IVRS system).

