Comparison will be between active group A receiving sargramostim on top of standard of care and control group B receiving standard of care. The change from baseline and daily change from baseline in oxygenation/respiratory parameter of P(A-a)O_2 gradient, ratio of $\text{PaO}_2/\text{FiO}_2$ and ratio of $\text{SpO}_2/\text{FiO}_2$ will be evaluated and summarized between group A and group B at Day 6. The difference of change from baseline between two groups will be tested by a t-test. In general, the last observed measurement prior to the first dose of study treatment occurred on Day 1 visit will be considered the baseline measurement. Day 6 is the primary analysis point. If the patient leaves hospital prior to the day 6 analysis point, oxygenation at day of discharge will be used as value for measuring primary endpoint.

The analyses described above will also be performed between group A (early 5 day intervention with sargramostim) and group D (late 5 day intervention with sargramostim). Change from baseline (D1) to Day 10, daily change from baseline (D1) at Day 10 in oxygenation/respiratory parameter of P(A-a)O_2

gradient, ratio of $\text{PaO}_2/\text{FiO}_2$ and ratio of $\text{SpO}_2/\text{FiO}_2$ will be summarized as well. A t-test will be conducted to compare the difference between the groups.

The same analyses will be repeated for pathological oxygenation parameter of P(A-a)O_2 gradient, ratio of $\text{PaO}_2/\text{FiO}_2$ and ratio of $\text{SpO}_2/\text{FiO}_2$ including summary of their value and change from baseline at Day 6 and Day 10. A waterfall plot will be used to represent the change from baseline and percentage change from baseline on Day 6 for 1) oxygenation parameter of P(A-a)O_2 gradient; 2) pathological oxygenation parameter of P(A-a)O_2 gradient; 3) ratio of $\text{PaO}_2/\text{FiO}_2$; 4) ratio of $\text{SpO}_2/\text{FiO}_2$. Percentage change from baseline of P(A-a)O_2 gradient and ratio of $\text{PaO}_2/\text{FiO}_2$ on Day 6 and follow-up will be summarized.

Reasons of missing AA gradient values on Day 6 will also be summarized.

The normal value of AA gradient for room air is calculated as: $2.5 + (0.21 \times \text{Age})$. All the results including change from baseline, and maximum change from baseline after 5 day intervention with sargramostim, normal AA gradient value for room air and flag of abnormality on Day 6 will be listed.

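### Section 7.1.1 defines group A, the active side of the primary comparison, by an outcome (no deterioration), which conflicts with its own count of 40 and with the rest of the protocol

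*Protocol*

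**What the plan says.** Section 7.1.1 lists the groups with their numbers. Group A, with 40 patients, is the active group: "treatment for initial 5 days, no deterioration after 5 days". Group B, also 40, is the "control group : no treatment with sargramostim in first 5 days", with nothing said about deterioration. Group C is made up of active patients who progress and may receive further intravenous drug from day 6. Group D is the corresponding set of controls. On the expected rate, the section says: "It is estimated that some 30% of patients might deteriorate and require non-invasive or invasive mechanical ventilation". It then turns this rate into a count for the active arm: "giving potentially rise to 12 patients that progress from group A to group C".

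The same section then states: "Comparisons between group A (early sargramostim) versus group B (no sargramostim) at day 6 will be important for reaching primary endpoint". Section 12.2 repeats the contrast: "Comparison will be between active group A receiving sargramostim on top of standard of care and control group B receiving standard of care". Section 4.2 also words the safety comparison as A versus B.

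Section 1.4.1 plans "40 in the active and 40 in the control group", and section 9.1 says "patients will be randomized in a 1:1 ratio".

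**The concern.** Whether a patient deteriorates is known only after randomisation. Read literally, the 7.1.1 definition lets an active patient who does badly leave group A, while a control who does equally badly still meets the definition of group B, even after entering group D. A comparison built that way would remove poor outcomes from one arm only and would lean towards sargramostim with no drug effect at all.

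The boundary is also soft. The trial is open-label, and entry to group C depends on the treating physician's assessment. The primary comparison should not depend on a label assigned in that way.

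**Working it through.** **Step 1: the section's own count.** Inputs: 40 randomised to active (1.4.1) and 30% expected to deteriorate (7.1.1).

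- 0.30 × 40 = 12, which reproduces the protocol's figure for moves from A to C.
- 40 − 12 = 28. If all 12 moved, group A as defined would have 28 patients, not 40.

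Both statements hold only if nobody moves. Twelve is a ceiling: the section calls it potential and makes it depend on the clinician's decision.

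**Step 2: how group A is used elsewhere in the protocol.**

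| Section | Use of the groups |
|---|---|
| 7.1.1, definition | Active, restricted to patients without deterioration |
| 7.1.1, count | 40, equal to everyone randomised to active |
| 3.1, 5.1, 12.2 | The active group, with no outcome condition |
| 4.1 | Primary endpoint reported by treatment arm |
| 9.2 | Group A is sampled before its first dose on Day 1 and inhales drug on days 1 to 5, so membership is known before any outcome |

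One clause stands against the rest. No sentence says outright that patients later labelled C or D stay in their assigned arms for A versus B.

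**Step 3: size of the bias if the clause were applied.** Null trials were simulated with 40 controls and 40 active patients. The k active patients ranked worst on a deterioration variable were removed, all 40 controls were kept, and the t-test named in 12.2 was run. The deterioration variable has correlation ρ with Day 6 oxygenation. The protocol gives neither ρ nor the number who would actually leave A, so both are assumptions: ρ from 0.3 to 1.0, and k = 4, 6 or 12.

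The expected shift is ρ × m(k), where m(k) is the mean of the best 40 − k of 40 standard normal values: m(4) = 0.188, m(6) = 0.267, m(12) = 0.486. For example, 0.3 × 0.188 = 0.056 SD and 1.0 × 0.486 = 0.49 SD.

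| k leaving A | ρ | Spurious benefit (SD) | False positives favouring sargramostim, two-sided 0.01 |
|---|---|---|---|
| 0 | any | 0 | 0.5% (nominal) |
| 4 | 0.3 | 0.06 | 1.0% |
| 4 | 1.0 | 0.19 | 5.0% |
| 6 | 0.3 | 0.08 | 1.3% |
| 6 | 1.0 | 0.27 | 9.7% |
| 12 | 0.3 | 0.15 | 2.3% |
| 12 | 0.5 | 0.24 | 5.8% |
| 12 | 0.7 | 0.34 | 13% |
| 12 | 1.0 | 0.49 | 34% |

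With the standard deviation of 10 units in section 12.1, 0.06 to 0.49 SD is 0.6 to 4.9 units. The row with ρ = 1.0 and k = 12 is an outer bound: it treats deterioration as identical to having the worst 30% of Day 6 values.

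**The case against.** A reader might infer that the protocol plans to leave deteriorating active patients out of the primary test, or that nothing in it points to analysis by randomised arm. The documents do not support either inference. Section 4.1 reports the primary endpoint by treatment arm, section 12.1 sizes the trial on 40 treated and 40 control patients, and section 9.2 uses group A as the assigned arm from Day 1.

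Timing points the same way. Group C forms only from day 6, which is when the primary endpoint is measured. Active patients who progress earlier switch to intravenous drug, and the endpoint in sections 3.1 and 4.1 covers intravenous as well as inhaled treatment, so early progressors appear to stay in. Excluding group C would mean applying a later label backwards, and no section directs that.

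It is also fair that section 12.2 refers to a separate statistical analysis plan and an mITT population. Detailed rules for analysis sets may sit there, so their absence from the protocol is not the point.

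All of this stands, and it limits the finding to a contradiction. It does not remove it. The outcome condition is written into the only formal definition of group A, and a later document could inherit it. Nor would the timing protect the comparison if the label were applied: patients who deteriorate after day 6 are likely to have worse Day 6 oxygenation already.

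**Conclusion.** The definition of group A in section 7.1.1 is wrong as written. It conditions the active side of the primary comparison on a post-randomisation outcome, puts no such condition on the control side, and disagrees with its own count (40 against 28 if all 12 move) and with the sections that treat A as the whole active arm.

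The whole-arm reading is the better supported one, and under it there is no bias from this source. Only if the clause were applied would the comparison be biased, always towards sargramostim: about 0.06 to 0.49 SD, with false positives in that direction of about 1% to 34% against a nominal 0.5%. That range rests on the assumed correlation (0.3 to 1.0) and the assumed number leaving A (4 to 12).

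This should be fixed as a contradiction in who is being compared. It is not evidence that the planned analysis is biased.

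**What to change.** In section 7.1.1, delete the no-deterioration condition from the definition of group A, leaving A as all patients randomised to active, n = 40.

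In section 12.2, add one sentence: A versus B compares all patients randomised to active, including any later labelled C, with all patients randomised to control, including any later labelled D, by assigned arm; for this comparison C and D are descriptive labels only.

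The cost is one deletion and one sentence. It needs no new data and changes neither the sample size nor any treatment rule. The statistical analysis plan should be checked to confirm that its population definitions say the same.

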7.1.2. Withdrawal and replacement of subjects

Subjects are free to withdraw from participation in the study at any time upon request.

An investigator may discontinue or withdraw a subject from the study for the following reasons:

- allergic reactions (anaphylactic shock) to sargramostim
- Pregnancy
- Progression to non-invasive or invasive mechanical ventilation and/or ARDS between screening and randomization
- Significant study intervention non-compliance
- If any clinical adverse event (AE), laboratory abnormality, or other medical condition or situation occurs such that continued participation in the study would not be in the best interest of the subject
- If the subject meets an exclusion criterion (either newly developed or not previously recognized) that precludes further study participation

In all cases, the reason why subjects are withdrawn must be recorded in detail in the eCRF and in the subject's medical records.

If a patient decides to leave hospital before day 6 of the study, for example because of clinical improvement, the oxygenation parameters at day of discharge will be used to calculate the primary endpoint measurement.

The following actions must be taken if a subject fails to return to the clinic for a required study visit (visit at 10-20 weeks after Day 1) :

- The site will attempt to contact the subject and reschedule the missed visit within 4 weeks and counsel the subject on the importance of maintaining the assigned visit schedule and ascertain if the subject wishes to and/or should continue in the study.
- Before a subject is deemed lost to follow-up, the investigator or designee will make every effort to regain contact with the subject (where possible, 3 telephone calls and, if necessary, a certified letter to the subject's last known mailing address or local equivalent methods). These contact attempts should be documented in the subject's medical record or study file.
- Should the subject continue to be unreachable, he or she will be considered to have withdrawn from the study with a primary reason of lost to follow-up.

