3.2. Secondary Objectives

- to study if early intervention with sargramostim is safe (number of AEs/SAEs)
- to study if early intervention with inhaled sargramostim affects clinical outcome defined by
 Duration of hospital stay
 Mean and median change in 6-point ordinal scale between day 1 and day 6
 Mean and median change in clinical sign score between day 1 and day 6
 Time to clinical sign score <6 maintained for 24h
 Mean and median change of SOFA score between day 1 and day 6 or between day 1 and day 10.
 Mean and median change NEWS2 score between day 1 and day 6 or between day 1 and day 10.
 Time to NEWS2 score less than 2 for at least 24h
- to study if early intervention with sargramostim affects the rate of nosocomial infection
- to study if early intervention with inhaled sargramostim affects progression to mechanical ventilation and/or ARDS
- to study if treatment with sargramostim affects all cause mortality rate at 28 days and 20 weeks post inclusion
- to study if treatment with sargramostim affects features of secondary haemophagocytic lymphohistiocytosis, as defined by Hs score (temp, organomegaly, cytopenia, triglycerides, fibrinogen, ferritin, AST and known immunosuppression)
- to study if treatment with sargramostim has a favourable effect on long term 10-20 week follow up

4. End Points + Time Points

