14.2. Reporting requirements

14.2.1. AE reporting

AE's will be recorded from the first drug administration until the end of the study, as defined in section 5.2.

Special attention will be given to those subjects who have discontinued the study for an AE, or who experienced a severe or a serious AE. All AE's should be recorded in the patient's file and in the CRF.

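### Section 7.1.2 lets the investigator withdraw randomised patients from the study for drug-related reasons and requires no follow-up afterwards, so data can be lost in an outcome-related, arm-dependent way

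*Protocol*

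**What the plan says.** Section 7.1.2 gives the power in these words: "An investigator may discontinue or withdraw a subject from the study for the following reasons". Four of the listed reasons can arise after randomisation and matter here:

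- Allergy: "allergic reactions (anaphylactic shock) to sargramostim"
- Adherence: "Significant study intervention non-compliance"
- Harm or laboratory change: "If any clinical adverse event (AE), laboratory abnormality, or other medical condition or situation occurs such that continued participation in the study would not be" (the sentence ends by making the patient's best interest the test)
- Eligibility: "If the subject meets an exclusion criterion (either newly developed or not previously recognized) that precludes further study participation"

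The list also has pregnancy, and progression to ventilation or ARDS between screening and randomisation. The one duty attached to a withdrawal is to record the reason. The contact steps later in the section are for patients who miss the 10-20 week visit.

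The exclusion criteria in Section 6.2 include a white cell count above 25,000 per microlitre and a ferritin limit: "Patients with serum ferritin > 2000 mcg/L (which will exclude ongoing HLH".

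Section 1.6 has patients stop the drug for unacceptable toxicity. Section 8.1.4 interrupts the drug at once for anaphylaxis or a severe adverse event. Neither takes the patient out of the study. Section 14.2.1, in contrast, foresees exit from the study: "Special attention will be given to those subjects who have discontinued the study for an AE". It does not say what that attention consists of.

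The secondary objectives include adverse-event counts, features of secondary HLH measured by HScore, and survival: "to study if treatment with sargramostim affects all cause mortality rate at 28 days and 20 weeks post inclusion".

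**The concern.** A patient who stops drug because of harm still has a Day 6 blood gas, scores, later adverse events and a survival outcome. All of these are needed to compare the arms as randomised. If the same event can also end study participation, those data may never be collected, and no analysis plan can recover them.

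The safety comparison is most exposed. Section 2.3 states that no safety data for this drug in COVID-19 existed, and Section 4.2 relies on comparing adverse events between groups A and B. With 40 patients per arm, a few withdrawals carry weight.

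**Working it through.** **Text check.** The protocol gives no withdrawal rate, so the main check sets the sections side by side.

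| Event after randomisation | Section 7.1.2 | Elsewhere | Where it can arise in days 1-5 |
|---|---|---|---|
| Allergic reaction or anaphylaxis | may be withdrawn from study | 8.1.4: drug interrupted | active arm only |
| Adverse event or toxicity | may be withdrawn, if in the patient's interest | 1.6 and 8.1.4: drug stopped | both arms; judged with the arm known (9.1, open label) |
| Non-compliance with study drug | may be withdrawn | no other rule | active arm only |
| White cells above 25,000 | may be withdrawn, if it precludes participation | 2.1 calls the drug a leukocyte growth factor | both arms; a drug effect is plausible |
| Ferritin above 2000 mcg/L | may be withdrawn, if it precludes participation | 9.4 footnote: an HScore component; 4.2: a marker of the HLH objective | both arms |

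Two things follow.

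1. Anaphylaxis and severe adverse events have two different consequences, and nothing says how the rules fit together.
2. No section requires the Day 6, score, adverse-event or survival assessments after an investigator's withdrawal. Section 14.2.1 records adverse events until the end of study as defined in 5.2, but Section 5.2.1 defines the individual end only for patients who complete. A withdrawn patient therefore has no stated end of recording.

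**Scale for mortality.** From Section 2.3, 15-20% of infected patients are admitted with severe respiratory symptoms, about 5% are invasively ventilated, and 40-50% of those die.

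- Deaths per infected patient: 0.05 × 0.40 = 0.020 to 0.05 × 0.50 = 0.025.
- Deaths per admitted patient: 0.020 / 0.20 = 0.10 to 0.025 / 0.15 = 0.167.
- Deaths per arm of 40: 40 × 0.10 = 4.0 to 40 × 0.167 = 6.7.
- One unobserved death: 1/40 = 2.5 percentage points; 1/6.7 = 15% to 1/4.0 = 25% of the arm's expected deaths.

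An assumed case shows the mechanism. Suppose 4 of 40 active patients are withdrawn with a 40% risk of death, and everyone else in both arms has 10%. The true active risk is (4 × 0.40 + 36 × 0.10) / 40 = 0.13, an excess of 3 points. Among the retained patients the expected difference is 0.

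**Scale for the primary endpoint.** Section 12.1 plans with a standard deviation of 10 units; its 10% target is read here as 10 units. If w active patients are lost and their mean is k standard deviations worse than that of the retained patients, the retained mean is too favourable by (w/40) × k × 10. Both w and k are assumptions.

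| w | k = 0.5 | k = 1 | k = 2 |
|---|---|---|---|
| 2 | 0.25 | 0.5 | 1.0 |
| 4 | 0.5 | 1.0 | 2.0 |
| 8 | 1.0 | 2.0 | 4.0 |

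Power is hardly touched. On the same inputs (two-sided 0.01, normal approximation) it is 0.971 with 40 per arm and 0.950 with 32 active patients. The stated 0.90 is not reproduced on this reading, but that does not bear on this point. The issue is bias and lost safety data.

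**The case against.** The other side has real points.

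- **Drug stop and study exit.** A reader of 7.1.2 alone might infer that the protocol treats them as one act throughout. It does not: 1.6 and 8.1.4 are drug-only rules. What stands is that 7.1.2 is not reconciled with them.
- **The rule is permissive and partly conditional.** The investigator may withdraw, and two of the reasons carry conditions. A ferritin or white-cell value over the limit after randomisation is therefore not in itself a ground for leaving.
- **Arm and direction.** It is tempting to conclude that losses fall mostly in the active arm and favour sargramostim. The documents make this likely, not certain. Ferritin is a severity marker that can also rise in controls, and losing such controls would work against sargramostim. If the study intervention is taken to include the sampling in Section 9.2, controls can be non-compliant too. Controls can also receive the drug from day 6. Patients who progress after randomisation are not on the withdrawal list.
- **Not all data need be lost.** Section 12.2 collects survival status to 20 weeks, Section 14.2.2 reports serious adverse events over the entire study period, and many values come from routine ward records (Section 9.2). Neither 12.2 nor 14.2.2 says that it covers withdrawn patients, and neither covers oxygenation or scores.
- **Frequency.** Section 7.2 expects high retention, and no withdrawal rate is given.

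These points limit the claim. They do not supply a follow-up rule.

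**Conclusion.** The point holds as a gap in the rule. Section 7.1.2 permits study withdrawal for reasons tied to the drug or to outcomes under study, it is unreconciled with 1.6 and 8.1.4, and nothing requires follow-up afterwards. In an open-label trial the resulting loss can depend on outcome and arm.

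Its size is unknown. The figure of 15-25% of an arm's expected deaths assumes that all ventilated patients are among those admitted, counts only deaths after ventilation, and takes trial patients to resemble admitted patients. A reader might instead apply the 3-7% mortality in Section 2.3 and get 1.2 to 2.8 deaths per arm, so that one death is 36-83% of them. That figure is for COVID-19 in general, not for hospitalised hypoxic patients, and it overstates the effect. The shifts of 0.25 to 4.0 units rest on assumed withdrawals.

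This should be fixed. It does not show that the trial's comparison is already biased.

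**What to change.** Amend 7.1.2 and reconcile it with 1.6, 8.1.4 and 14.2.1, so that stopping study drug and leaving the study are separate acts. The amendment should neither set nor change any ground for stopping the drug.

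- After randomisation, limit study withdrawal to withdrawal of consent or loss to follow-up.
- State that every randomised patient in either arm, whether or not drug is stopped, continues with the Day 6 or discharge blood gas and scores, adverse-event and serious adverse-event recording, Day 28 and week 20 survival status, and the 10-20 week visit, unless consent is withdrawn.
- Move progression between screening and randomisation to the screen failures of Section 6.2.1.
- Add an eCRF field for drug discontinuation, separate from study withdrawal.

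The cost is one amended paragraph, one eCRF field and a few more follow-up contacts. Patients can still refuse.
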